3.1.5. Pharmacokinetic Analysis Set

The Pharmacokinetic (PK) Analysis Set includes all subjects in the Safety Analysis Set who have evaluable on-study PK measurements. This is the primary analysis set for all PK analyses.

3.2. Subject Grouping

For analyses based on the FAS and PP Analysis Set, subjects will be grouped according to the treatment to which they were randomized. For analyses based on the Safety Analysis Set, subjects will be grouped according to the actual treatment received. The actual treatment received will differ from the randomized treatment only when their actual treatment differs from randomized treatment for the entire treatment duration.

For the PK Analysis Set, subjects will be grouped according to the actual treatment they received.

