1.2. Study Design

This is a randomized, double-blind, placebo-controlled study evaluating the effect of presatovir on efficacy, PK, safety, and tolerability in HCT recipients with RSV LRTI.

All subjects will be permitted to receive the standard of care therapy for RSV infection per their local medical practices, in addition to the investigational medicinal product (IMP).

Approximately 60 subjects will be enrolled from approximately 45 international HCT centers.

[figure not shown]
Subjects will be randomized in a 1:1 ratio to receive IMP (presatovir or placebo) and will be stratified by 2 factors:

- Supplemental O₂ requirement (≤ 2 L/min or > 2 L/min) at the time of randomization
- Treatment of current RSV infection (yes or no) with ribavirin (oral, intravenous, or aerosolized)

A single dose of 200 mg (four 50 mg tablets) of presatovir or placebo will be administered on Study Days 1, 5, 9, 13, and 17. The study will consist of the following visits: screening (Day -1), baseline/randomization/IMP administration (Day 1), optional Visit 3 (Day 3), Visit 4 (Day 5),

Visit 5 (Day 7), Visit 6 (Day 9), Visit 7 (Day 13), Visit 8 (Day 17), Visit 9 (Day 22), and end of study (Day 28). Four additional visits at Days 35, 42, 49, and 56 will only be completed for subjects who consent to the optional extended viral monitoring and test positive for RSV at Visit 9 (Day 22) (see Figure 1-1).

Figure 1-1. **Study Visits**

[figure not shown]

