3.1.3. Per Protocol Analysis Set

The Per-Protocol (PP) Analysis Set includes subjects in the FAS who meet the following criteria:

- Did not violate the following major inclusion criteria (IC)
 - IC #2: Received an autologous or allogeneic HCT using any conditioning regimen
 - IC #3: Chest X-ray obtained < 48 hours prior to Screening
 - IC #4: Documented RSV in both the upper and lower respiratory tract as determined by local testing collected \leq 6 days prior to Day 1

- Did not administered invalid (eg, expired, damaged, quarantined, improperly stored) study drug
- Not be dispensed incorrect study drug (wrong bottle) or drug from another study
- Missed < 1 dose (200 mg) in the first 9 study days
- Missed < 3 nasal swab samples over the course of the study

The PP Analysis Set is the secondary analysis set for efficacy analyses.

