3.1.4. Safety Analysis Set

The Safety Analysis Set includes subjects who took at least 1 full dose of study drug. This is the primary analysis set for safety analyses.

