7.1.5. Treatment-Emergent Adverse Events

7.1.5.1. Definition of Treatment-Emergent Adverse Events

Treatment-emergent adverse events (TEAE) are defined as 1 or both of the following:

- Any AEs with an onset date on or after the study drug start date up to the Day 28, or up to 28 days if a subject withdraws early (prior to Day 28) from the study
- Any AEs leading to premature discontinuation of study drug

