7.1.6. Summaries of Adverse Events and Deaths

Treatment-emergent (TE) AEs will be summarized based on the Safety Analysis Set.

The number and percentage of subjects who experienced at least 1 TEAE will be provided and summarized by SOC and PT, and treatment group. For other AEs described below, summaries will be provided by SOC, PT, and treatment group:

- TEAE by maximum severity
- TEAEs of Grade 3 or higher (by maximum severity)
- TEAEs of Grade 2 or higher
- All TE treatment-related AEs
- All TE treatment-related AEs by maximum severity
- TE treatment-related AEs of Grade 3 or higher (by maximum severity)
- TE treatment-related AEs of Grade 2 or higher
- All TE SAEs
- All TE treatment-related SAEs
- All TEAEs leading to premature discontinuation of study drug

- All TEAEs leading to premature discontinuation of study
- All AEs leading to death (ie, outcome of death)

A brief, high-level summary of AEs described above will be provided by treatment group and by the number and percentage of subjects who experienced the above AEs. All deaths observed in the study will be also included in this summary.

Multiple events will be counted only once per subject in each summary. Adverse events will be summarized and listed first in alphabetic order of SOC and HLT within each SOC (if applicable), and then by PT in descending order of total frequency within each SOC. For summaries by severity grade, the most severe grade will be used for those AEs that occurred more than once in an individual subject during the study.

In addition to the above summary tables, all TEAEs, TE treatment-related AEs, and TE SAE will be summarized by PT only, in descending order of total frequency.

In addition, data listings will be provided for the following:

- All AEs, indicating whether the event is treatment emergent
- All AEs of Grade 3 or higher
- All AEs of Grade 2 or higher
- SAEs
- Deaths
- All AEs leading to death (ie, outcome of death)
- AEs leading to premature discontinuation of study drug
- AEs leading to premature discontinuation of study

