12.3. Listings

Listing	Title	Analysis Set
16.1.6	Subjects Who Received Study Drug from Specific Batches	Safety Analysis Set
16.1.7	Randomization Schema and Codes	All Randomized Analysis Set
16.2.1.1	Subject Profiles	All Randomized Analysis Set
16.2.1.2	Enrollment	All Randomized Analysis Set
16.2.1.3	Subject Disposition	All Randomized Analysis Set
16.2.1.4	Reasons for Screen Failure	Subjects Screened but Not Enrolled
16.2.2.1	Eligibility Criteria Deviations	All Randomized Analysis Set
16.2.2.2	Important Protocol Deviations	All Randomized Analysis Set
16.2.2.3	Randomization Stratification Discrepancies Between IWRS and Clinical Database	All Randomized Analysis Set
16.2.2.4	Subjects who Received Incorrect Study Drug	All Randomized Analysis Set
16.2.3.1	Subjects Excluded from Any Analysis Set	All Randomized Analysis Set
16.2.3.2	Subjects Who were in the Full Analysis Set but Excluded from the Per Protocol Analysis Set	Full Analysis Set
16.2.4.1	Demographics	All Randomized Analysis Set
16.2.4.2	Baseline Characteristics	All Randomized Analysis Set
16.2.4.3.1	Hematopoietic Cell Transplant Medical History	All Randomized Analysis Set
16.2.4.3.2	Medical History	All Randomized Analysis Set
16.2.4.4.1	Prior and Concomitant Medications	All Randomized Analysis Set
16.2.4.4.2	Prior and Concomitant Ribavirin	All Randomized Analysis Set
16.2.5.1	Study Drug Administration	All Randomized Analysis Set
16.2.5.2	Subjects Who Prematurely Discontinued Study Drug	All Randomized Analysis Set
16.2.5.3	Study Drug Accountability	All Randomized Analysis Set
16.2.5.4	Plasma Pharmacokinetic Sampling Details and Concentrations	PK Analysis Set
16.2.6.1	Viral Load Measurements	Full Analysis Set
16.2.6.2	Hospitalizations and ICU	Full Analysis Set
16.2.6.3	Oxygen Saturation	Full Analysis Set
16.2.6.4	Supplemental Oxygen	Full Analysis Set
16.2.6.5	Supplemental Oxygen Use Prior to RSV Infection	Full Analysis Set
16.2.6.6	Mechanical Ventilation	Full Analysis Set
16.2.6.7	Healthcare Related Efficacy Endpoints	Full Analysis Set
16.2.7.1	All Adverse Events	Safety Analysis Set

Listing	Title	Analysis Set
16.2.7.2.1	Deaths	All Randomized Analysis Set
16.2.7.2.2	Adverse Events Leading to Death	Safety Analysis Set
16.2.7.3	Serious Adverse Events	Safety Analysis Set
16.2.7.4.1	Adverse Events with Severity of Grade 3 or Higher	Safety Analysis Set
16.2.7.4.2	Adverse Events with Severity of Grade 2 or Higher	Safety Analysis Set

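### The safety grouping rule in SAP 3.2 would leave a placebo subject given presatovir at one to four of five doses in the placebo column

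*SAP*

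**What the plan says.** SAP 3.2 sets the principle for safety: "For analyses based on the Safety Analysis Set, subjects will be grouped according to the actual treatment received". The next sentence narrows it: "The actual treatment received will differ from the randomized treatment only when their actual treatment differs from randomized treatment for the entire treatment duration".

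The provisions that decide what this means in practice are these:

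- **Regimen (SAP 1.2).** A single dose "of presatovir or placebo will be administered on Study Days 1, 5, 9, 13, and 17", so there are five separate occasions on which the product could be right or wrong.
- **Entry to the safety set (SAP 3.1.4).** "The Safety Analysis Set includes subjects who took at least 1 full dose of study drug". A subject with mixed exposure is included.
- **Event window (SAP 7.1.5.1).** "Any AEs with an onset date on or after the study drug start date up to the Day 28". The window does not depend on which product preceded the event.
- **Tables.** Under SAP 7.1.6, treatment-emergent "AEs will be summarized based on the Safety Analysis Set". The laboratory summaries (7.2), the cardiac events of interest (7.1.7) and the ECG and troponin tables in 12.1 use the same set.
- **Dispensing errors.** The Per-Protocol criteria in 3.1.3 include "Not be dispensed incorrect study drug (wrong bottle) or drug from another study", and 12.3 plans Listing 16.2.2.4, "Subjects who Received Incorrect Study Drug". Neither changes the safety grouping, and SAP 3 has listings show the randomised group.

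**The concern.** The two sentences in 3.2 pull apart. The first promises as-treated safety grouping. The second makes it as-randomised for everyone except a subject whose every dose was of the other product. For a regimen given at one visit the two would coincide; for five visits they do not.

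The consequence is one-sided. If a placebo subject is given presatovir at some visits, later events that may be due to presatovir are tabulated as control events, and the comparison moves towards no difference. Safety is a secondary objective (1.1), and cardiac events have their own analysis (7.1.7, Appendix 2). The arms are small, so one subject can matter. The final tables also carry more of the safety assessment than was planned: one data monitoring review took place, after about 25% of planned subjects, and no further meetings were scheduled (2.1, 7.7).

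**Working it through.** There is no stated figure to reproduce; the point rests on a classification rule. The rule was applied to all possible dosing histories and its effect on an incidence was then worked out.

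**Step 1: what the rule does.** Take a placebo-randomised subject who takes *m* doses, *k* of them presatovir. Under 3.2 the subject moves to presatovir only if *k* = *m*. For a full course, *m* = 5:

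| Presatovir doses *k* | Column under 3.2 | Column under an any-presatovir-dose rule |
|---|---|---|
| 0 | placebo | placebo |
| 1, 2, 3 or 4 | placebo | presatovir |
| 5 | presatovir | presatovir |

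There are 2^5 = 32 possible sequences of right and wrong product. One is entirely right, one entirely wrong and 30 are mixed. The rule in 3.2 moves the subject in 1 of the 32. These are counts of patterns, not probabilities. A subject who stops early after *m* doses stays under placebo with up to *m* − 1 presatovir doses, and moves if every dose taken was wrong.

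**Step 2: how much follow-up is affected.** Days from first presatovir exposure to Day 28, inclusive, are 28 − day + 1. First exposure on Day 1, 5, 9, 13 or 17 gives 28, 24, 20, 16 or 12 days reported as placebo experience.

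**Step 3: the reverse mix-up.** A presatovir-randomised subject given placebo at one to four visits stays under presatovir under 3.2. An any-presatovir-dose rule leaves that subject there too, so only mixed-exposure placebo subjects change column.

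**Step 4: size.** The planned 60 subjects at 1:1 (1.2, 1.3) give 60/2 = 30 per arm, assuming all are dosed. Suppose two of the 30 presatovir-randomised subjects have a given event, *s* placebo-randomised subjects have mixed exposure and all *s* have the event, and no other placebo subject has it. The SAP gives no value for *s*; 1 to 3 is an assumed range.

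| *s* | Under 3.2: presatovir v placebo | Gap (points) | Any-presatovir-dose: presatovir v placebo | Gap (points) |
|---|---|---|---|---|
| 1 | 2/30 (6.7%) v 1/30 (3.3%) | 3.3 | 3/31 (9.7%) v 0/29 (0%) | 9.7 |
| 2 | 2/30 (6.7%) v 2/30 (6.7%) | 0 | 4/32 (12.5%) v 0/28 (0%) | 12.5 |
| 3 | 2/30 (6.7%) v 3/30 (10.0%) | −3.3 | 5/33 (15.2%) v 0/27 (0%) | 15.2 |

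If the one mixed subject does not have the event, the two rules give 2/30 (6.7%) v 0/30 and 2/31 (6.5%) v 0/29, which is practically the same. With *s* = 0 the rules agree exactly.

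**The case against.** The strongest defence is that 3.2 states a convention openly and in advance. It defines its own term, is unambiguous, and is one of several possible choices (entire course, majority of doses, any dose). That stands: this is a poor choice, not an omission or a slip.

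The problem is also contingent. A reader might infer from the Per-Protocol criterion and Listing 16.2.2.4 that crossover between arms occurred or was expected. The documents do not support that. A wrong bottle may hold the assigned product, and a planned listing does not show that anyone will appear in it.

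The listings give partial protection. Incorrect study drug (16.2.2.4), drug administration (16.2.5.1) and adverse events (16.2.7.1, 16.2.7.3) would let a reader trace an affected subject, which is feasible with about 30 per arm. The incidence tables would still not change.

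A reader might also extend the point to pharmacokinetics and infer that a placebo subject's presatovir concentrations would be left out, or that a mixed presatovir subject would add values below the limit of quantification. The documents do not support this either. The pharmacokinetic sentence in 3.2 is a separate paragraph without the whole-course qualifier, and SAP 8 includes all subjects with concentration data. Samples on Days 5 to 17 are taken before dosing (Appendix 1), and no half-life is given from which to say they would be unquantifiable.

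Finally, an any-dose rule has its own misattribution. A placebo subject given presatovir only on Day 17 would have events from Days 1 to 16 counted under presatovir although they came before exposure. This stands, and is why the fix includes a supplementary table.

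**Conclusion.** The point holds for the safety tables. On its plain wording, 3.2 keeps a full-course placebo subject with one to four presatovir doses under placebo, and nothing in the safety sections or the table list overrides it. If such a subject exists and has the event of interest, the table understates the difference between arms. In the one-subject illustration the gap is 3.3 points instead of 9.7.

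This rests on three conditions: that a mix-up between products occurs, that the affected subject was randomised to placebo, and that the subject has the event. The SAP reports no such case, and without one the effect is nil. It would be too strong to say that the rule hides harm in general, or that the safety results are biased. The matter is a cheap improvement to a stated rule. The efficacy sets are not affected, and the documents do not support carrying the criticism over to pharmacokinetics.

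**What to change.** In SAP 3.2, for the Safety Analysis Set only, replace the whole-course condition with a sentence to this effect: a subject who received at least one dose of presatovir is grouped under presatovir; all other subjects are grouped under placebo. Add that, if any subject had mixed exposure, a supplementary adverse event table will assign events by the product received before onset. Leave the Full Analysis Set and the Per-Protocol set grouped as randomised.

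Write the rule before the blind is broken, so that it is not chosen with knowledge of which subjects or events it moves. SAP 3.1 already settles membership of the analysis sets at that point.

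The cost is one sentence and, only if needed, one table. There are two downsides. An affected subject's safety group will differ from the randomised group. In the main table, events before that subject's first presatovir dose will count under presatovir; the supplementary table shows how many there are.

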3.3. Strata and Covariates

Subjects will be randomly assigned to treatment groups via the interactive web response system (IWRS) in a 1:1 ratio using a stratified randomization schedule. Stratification will be based on the following parameters:

- Supplemental O₂ requirement (\leq 2 L/min or $>$ 2 L/min) at the time of randomization
- Treatment of current RSV infection (yes or no) with ribavirin (oral, intravenous, or aerosolized)

If there are discrepancies in stratification factor values between the IWRS and the clinical database, the values recorded in the clinical database will be used for analyses.

Efficacy endpoints will be evaluated using stratification factors as covariates for analyses, as specified in Section 6. In the event the number of subjects within a stratum of the stratification factor is small (eg. ≤ 4 subjects), the stratum will be collapsed with the adjacent stratum for the analysis.

For efficacy endpoints, the baseline value of the efficacy variables will be included as a covariate in the efficacy analysis model.

3.4. Examination of Subject Subgroups

The primary and secondary efficacy endpoints will be examined using the following subgroups:

- Actual ribavirin use at the first dosing date (Yes or No)
- Supplemental O₂ requirement (≤ 2 L/min or > 2 L/min) at the time of randomization

The primary efficacy endpoint will also be examined by RSV type (RSV A or RSV B).

The safety endpoints will be examined using the following subgroups:

- Age (< 65 years and ≥ 65 years)
- Sex (male and female)

3.5. Multiple Comparisons

In order to account for multiple hypothesis testing of endpoints, a sequential testing procedure will be used to control the Type 1 error rate of 0.05 across the primary and secondary endpoints. The primary endpoint analysis will serve as the gatekeeper for the secondary analyses, ie, the primary efficacy hypothesis must be rejected at the 2-sided 0.05 significance level before the efficacy hypotheses for the secondary efficacy endpoints can be evaluated.

If the primary null hypothesis is rejected, then the following secondary endpoints will be tested sequentially at 2-sided $\alpha = 0.05$ significance level in the order listed below based upon the closed testing procedure {Dmitrienko 2003}.

- Number of supplemental O₂ free days through Day 28
- Proportion of subjects developing respiratory failure (of any cause) requiring mechanical ventilation (invasive or noninvasive) through Day 28
- Proportion of all-cause mortality among all subjects through Day 28

3.6. Missing Data and Outliers

3.6.1. Missing Data

In general, missing data will not be imputed unless methods for handling missing data are specified. Exceptions are presented in this document.

For missing last dosing date of study drug, imputation rules are described in Section 4.2.1. The handling of missing or incomplete dates for AE onset is described in Section 7.1.5.2 and for prior and concomitant medications in Section 7.4. The handling of missing data in analyses of the efficacy endpoints is discussed in Section 6.

3.6.2. Outliers

Outliers will be identified during the data management and data analysis process, but no sensitivity analyses will be conducted. All data will be included in the data analyses.

3.7. Data Handling Conventions and Transformations

In general, age (in years) on the date of the first dose of study drug will be used for analyses and presentation in listings. If an enrolled subject was not dosed with any study drug, the randomization date will be used instead of the first dosing date of study drug. For screen failures, the date the informed consent was signed will be used for age calculation. If only the birth year is collected on the eCRF, “01 January” will be used for the unknown birth day and month for the purpose of age calculation. If only birth year and month are collected, “01” will be used for the unknown birth day.

Non-PK data that are continuous in nature but are less than the lower limit of quantitation (LOQ) or above the upper LOQ will be imputed as follows:

- A value that is 1 unit less than the LOQ will be used to calculate descriptive statistics if the datum is reported in the form of “ $< x$ ” (where x is considered the LOQ). For example, if the values are reported as < 50 and < 5.0 , values of 49 and 4.9, respectively, will be used to calculate summary statistics. An exception to this rule is any value reported as < 1 or < 0.1 , etc. For values reported as < 1 or < 0.1 , a value of 0.9 or 0.09, respectively, will be used to calculate summary statistics.
- A value that is 1 unit above the LOQ will be used to calculate descriptive statistics if the datum is reported in the form of “ $> x$ ” (where x is considered the LOQ). Values with decimal points will follow the same logic as above.
- The LOQ will be used to calculate descriptive statistics if the datum is reported in the form of “ $\leq x$ ” or “ $\geq x$ ” (where x is considered the LOQ).

If methods based on the assumption that the data are normally distributed are not adequate, analyses may be performed on transformed data (eg, log-transformed data) or nonparametric analysis methods may be used, as appropriate.

Plasma concentration values that are below the limit of quantitation (BLQ) will be presented as “BLQ” in the concentration data listing. Values that are BLQ will be treated as 0 at predose time points, and one-half the value of the LOQ at post-baseline time points.

The following conventions will be used for the presentation of summary and order statistics:

- If at least 1 subject has a concentration value of BLQ for the time point, the minimum value will be displayed as “BLQ.”
- If more than 25% of the subjects have a concentration data value of BLQ for a given time point, the minimum and Q1 values will be displayed as “BLQ.”
- If more than 50% of the subjects have a concentration data value of BLQ for a given time point, the minimum, Q1, and median values will be displayed as “BLQ.”
- If more than 75% of the subjects have a concentration data value of BLQ for a given time point, the minimum, Q1, median, and Q3 values will be displayed as “BLQ.”
- If all subjects have concentration data values of BLQ for a given time point, all order statistics (minimum, Q1, median, Q3, and maximum) will be displayed as “BLQ.”

3.8. Analysis Visit

3.8.1. Definition of Study Day

Study day will be calculated from the first dosing date of study drug and derived as follows:

- For post-dose study days: Assessment Date – First Dosing Date + 1
- For days prior to the first dose: Assessment Date – First Dosing Date

Therefore, study day 1 is the day of first dose of study drug administration.

3.8.2. Analysis Visit

The nominal visit as recorded on the eCRF will be used when data are summarized by visit. Any data relating to unscheduled visits will not be assigned to a particular visit or time point. However, the following exception will be made:

- An unscheduled visit prior to the first dosing of study drug may be included in the calculation of the baseline value, if applicable.
- Unscheduled visits after the first dose of study drug will be included in determining the maximum post-baseline toxicity grade.

- For subjects who prematurely discontinue from the study, early termination (ET) data will be assigned to the next scheduled visit where the respective data were scheduled to be collected.
- Data collected on an extended viral load monitoring visit will be summarized as a separate visit, and labeled as Day 35, 42, 49, or 56.

